4.1. Primary Objective

As the primary objective, this trial will test the hypothesis that lithium is superior to placebo for the prevention of suicidal self-directed violence. This will be accomplished by comparing event-free survival distribution in the two treatment groups.

4.2. Primary Endpoint

The primary outcome measure is time from randomization for treatment allocation to the first episode of suicidal self-directed violence assessed over one year follow up period. Episode of suicidal self-directed violence include (1) non-fatal suicide attempts, (2) interrupted attempts, (3) hospitalizations specifically to prevent suicide, and (4) deaths from suicide. All potential primary endpoints identified via CRFform data (mostly through the serious adverse event reporting or Columbia Follow Up form), will be evaluated by two independent adjudicators. If the adjudicators do not agree in deciding the event to be (or not to be) the primary endpoint event, then a third adjudicator will evaluate the same information and serve as a tie-breaker.

4.3. Statistical Methods for Primary Efficacy Analysis

Primary efficacy analysis will include the modified intention to treat sample as defined in section 3.3 above.

The primary hypothesis can be stated as follows.

Under the null hypothesis: The 1-year event rate is 15% and the two treatment groups do not differ in their time to event hazard rates.

Under the alternative hypothesis: The 1-year event rate is 9.45% for patients treated with lithium and 15% for patients in the placebo group, resulting in an absolute reduction from 15% to 9.45% = 5.55% and a relative reduction of $(15 - 9.45)/15 = 37\%$. The group on lithium augmentation has a lower hazard rate than the placebo augmentation group with a hazard ratio for lithium therapy compared to control therapy lower than or equal to 0.61.

We will test this hypothesis with a two sided log rank test at 90% power and 4.8% Type I error (i.e., 5% overall error allows for one interim test at 0.2%). Null hypothesis will be rejected if the hazard ratio exceeds $1/0.61 = 1.64$ or falls below 0.61.

A significant difference showing that the lithium augmentation compared to placebo decreases the hazard of suicidal self-violence will be regarded as a positive result, whereas a result that shows lithium augmentation does not significantly differ from placebo or significantly increases the hazard rate relative to placebo will be regarded as a negative result.

Log rank test will be followed by Cox proportional hazards regression modeling to provide the hazard rates, their ratio and the 95% confidence interval about the ratio.

We will test the proportional hazards assumption by including a time*treatment interaction term in the model and use graphic methods to study goodness of fit as described in Anderson et. al., 1991.

The SAS code for the primary analysis is as follows, where, tx is coded as {1=lithium, 0=placebo}, event is coded as {1=adjudicated outcome, 0=otherwise}, and FUdays is counting number of days from randomization date to the first occurrence of (adjudicated outcome, death, 12 month date, or last study visit/contact date).

Log-Rank Test:

```
title "Survival Estimates by Month";
proc lifetest data=endpt plots=(s); time FUdays*event(0); strata tx; run;
quit;
proc lifetest data=endpt method=life plots=(ls) intervals=30 90 120 150
180 210 240 270 300 330 365; time FUdays*event(0); strata tx; run; quit;

title "Survival Estimates by Month";
proc lifetest data=endpt method=life plots=s intervals=30 90 120 150 180
210 240 270 300 330 365; time FUdays*event(0); strata tx; run; quit;

title "Hazard Estimates by Month";
ods output lifetableestimates=life(keep=stratum lowertime uppertime
hazard);
proc lifetest data=endpt method=life intervals=30 90 120 150 180 210 240
270 300 330 365; time FUdays*event(0); strata tx; run; quit;
data life; set life; where hazard ne .;
time=lowertime+(uppertime-lowertime)/2; keep stratum time hazard; run;
proc export data=life outfile="life.csv" dbms=CSV replace; run;

title "Basic model - Exponential";
proc lifereg data=endpt; model FUdays*event(0)=tx5fu / dist=exp; run;
quit;
```

Cox-Proportional Model:

```
*CHECK PROPORTIONAL HAZARDS FOR TREATMENT*;
title 'Basic model - Cox model with treatment*time interaction';
ods select ParameterEstimates;
proc phreg data=endpt; where FUdays>0;
```

```

    model FUdays*event(0)=tx int/ rl;
    int=tx*log(FUdays);
    Proportionality: test int;
run; quit;

proc phreg data=endpt; where FUdays>0;
    model FUdays*event(0)=tx;
    output out=propcheck ressch=schres;
run; quit;
proc sgplot data=propcheck; loess x=FUdays y=schres / clm; run;

title "Basic model - Cox model";
proc phreg data=endpt; model FUdays*event(0)=tx / rl;
run; quit;

```

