The formal hypothesis test is two-sided allowing for lithium augmentation therapy to be either more or less effective than placebo augmentation of enhanced suicide prevention management. However, the study of lithium will only be viewed as successful if patients augmented with lithium have a significantly lower hazard of repeated events than patients not treated with lithium.

We will test this hypothesis with a log rank test, followed by Cox proportional hazards regression modeling to provide the hazard rates, their ratio and the 95% confidence interval

about the ratios. We will also fit a random effects or frailty model to investigate potential heterogeneity of effect due to site variability (Glidden et al., 2004; Hougaard, 1991).

Interim Analysis

We will conduct one interim analysis after half of the participants have completed their 12 month follow up. Assuming a uniform rate of enrollment, it will take 1.5 years to enroll half the sample. Allowing for the last patient to accrue 12 months of follow-up, the interim analysis should take place approximately 2.5 years after initiation of enrollment, at which time, after adjusting for attrition, there should be a sample of 746 evaluable subjects, (373 in each group).

Projecting the same event rate in this sub-sample we expect a 15% repeat rate or 112 events (56 events in each group) under the interim null hypothesis that event rates are equal in the intervention and placebo groups. Under the interim alternative hypothesis, the absolute reduction from 15% to 5.3% is $(15-5.3) = 9.7\%$, the relative reduction is $(15-5.3)/15 = 65\%$, and the hazard ratio (treatment hazard rate/control hazard rate) is 0.34.

Using the O'Brien-Fleming procedure, (Turnbull & Jennison, 2000), this analysis will have a Type I error of 0.2%, which negligibly decreases the overall Type I error for the study and has virtually no effect on the power for primary analysis. The interim analysis is two-sided, and the interim null hypothesis will be rejected if the hazard ratio exceeds $1/0.34 = 2.94$ or falls below 0.34.

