8.3.5. Section D: Safety Assessment (CLOSED SESSION ONLY)

Table D1. Rates of Non-Serious Related Adverse Events (NAEs), by Site and Treatment
Table D2. Rates of Serious Adverse Events (SAEs), by Site and Treatment
Table D3. **Reported in OPEN SESSION only**
Table D4. Summary of Serious Adverse Events (Form B15), by Treatment
Table D5. Related Non-Serious Adverse Events by System Organ Class, by Treatment
Table D6. Serious Adverse Events by System Organ Class, by Treatment
Table D7. Deaths Reported, by Treatment

9. Analytic Tables not included in the Data Monitoring Committee Reports

Following analytic tables will be generated annually and made available to the study team, Upon request of the DMC at the initial meeting these tables will not be included in the DMC report.

Table X1. Military Service

Table X2. Medical and Psychiatric History

Table X3. MINI Module Assessment

Table X4. Baseline Physical Assessments

Table X5. Baseline Laboratory Results

Table X6. Baseline Psychiatric Measures

Table X7. Baseline Substance Use (SCID-SUD)

Table X8. Concomitant Medications

10. Sample Size and Power

CSP590 is targeted to enroll a total of 1862 subjects, and approximately 40% of the enrolled sample is expected to terminate early (i.e., 20% complete data loss), thereby resulting in an analytic sample of 1490 evaluable subjects. With the evaluable study sample equally allocated to the 2 treatment arms, the study is powered to detect at least a 37% reduction in the one year outcome event rate.

Expected event rates used in sample size estimation to achieve 90% statistical power for hypothesis testing were 15% re-attempt rate in the placebo group and 9.45% re-attempt rate in the lithium group. Justification for selecting these rates to estimate sample size and power are provided in the protocol.

The results for the primary outcome measure will be analyzed by a two-sided log-rank test to detect either a hazards ratio that exceeds $1/0.61=1.64$ or is less than 0.61, i.e., the test has 90% power to detect a hazard ratio of 1.64 or larger or 0.61 or less.

These estimations are adjusted for an O'Brien-Fleming stopping rule with one interim and one final test of hypothesis, and allow for an overall two-sided type I error of 5% for the hypothesis being tested. Hence, the interim primary hypothesis will be tested at $p=0.002$ level (allowing for 0.2% Type I error), and the final primary hypothesis will be tested at $p=0.048$ level (allowing for 4.8% Type I error).

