Tables 2 below consider three scenarios for possible shift in statistical power, specifically (a) in the event that an intervention effect different from the projected 37% reduction is observed, (b) in the event that the sample size for the study falls either above or below the targeted 1490 evaluable subject mark, and (c) in the event that the event rate is below the expected 15% in the placebo group. This study will have greater than 80% statistical power at 5% overall error if the observed effect is as low as 33% reduction, if the final evaluable sample is as low as 1200 subjects, or if we observe an event rate as low as 12% in the placebo group.

Table 2: Evaluation of variability in Statistical Power assuming 5% Overall Type I error.

(a) Change in statistical power for fixed sample size and a range of effect sizes

		Event Rates				
Evaluable N	N per arm	Placebo	Active	#Events	Effect	Power
1490	745	15%	11%	190	30%	73%
1490	745	15%	10%	188	31%	77%
1490	745	15%	10%	187	33%	81%
1490	745	15%	10%	185	35%	85%
*1490	745	15%	9.5%	182	37%	90%
1490	745	15%	9%	179	40%	94%

(b) Change in statistical power for fixed effect size and a range of sample sizes

		Event Rates				
Effect	Placebo	Active	Evaluable N	N per arm	#Events	Power
37%	15%	9.5%	1700	850	208	93%
*37%	15%	9.5%	1490	745	182	90%
37%	15%	9.5%	1400	700	171	88%
37%	15%	9.5%	1200	600	147	83%
37%	15%	9.5%	1100	550	134	79%
37%	15%	9.5%	1000	500	122	75%

(c) Change in statistical power for fixed effect and sample size and a range of event rates

Total N	N per arm	Event Rates		#Events	Effect	Power
		Placebo	Active			
*1490	745	15%	9.5%	182	37%	90%
1490	745	14%	8.8%	170	37%	88%
1490	745	13%	8.2%	158	37%	85%
1490	745	12%	7.6%	146	37%	82%
1490	745	11%	6.9%	134	37%	78%
1490	745	10%	6.3%	121	37%	73%

*Highlight indicates parameters proposed in CSP590

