10.1. Interim Analysis

We will conduct one interim analysis after half of the participants have completed their 12 month follow up. This analysis is projected to take place approximately 2.5 years after initiation of enrollment (assuming it will take 1.5 years to enroll half the sample and allow 12 months of follow-up). After adjusting for attrition, a sample of 746 evaluable subjects, (373 in each group), is expected to be included in the analysis.

Projecting the same event rate in this sub-sample we expect to observe a 15% or 112 events (56 events in each group) under the interim null hypothesis that event rates are equal in the treatment groups. Under the interim alternative hypothesis, the absolute reduction from 15% to 5.3% is $(15-5.3) = 9.7\%$, the relative reduction is $(15-5.3)/15 = 65\%$, and the hazard ratio (treatment hazard rate/control hazard rate) is 0.34. The interim log-rank test is two-sided, and the interim null hypothesis will be rejected if the hazard ratio exceeds $1/0.34 = 2.94$ or falls below 0.34. Using the O'Brien-Fleming procedure, (Turnbull & Jennison, 2000), this analysis will have a Type I error of 0.2%.

We will confer with the Data Monitoring Committee members and the program leadership for potential stopping guidelines based on results from interim efficacy analysis.

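### Three sentences (SAP 4.3, SAP 10.1, Protocol VII interim) give detectable hazard ratios as rejection cut-offs, which contradicts the stated log-rank levels of 0.048 and 0.002

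*SAP*

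**What the plan says.** SAP 4.3 specifies a "two sided log rank test at 90% power and 4.8% Type I error". The sentence that follows is "Null hypothesis will be rejected if the hazard ratio exceeds $1/0.61 = 1.64$ or falls below 0.61". The next paragraph then classifies the outcome by significance alone: "A significant difference showing that the lithium augmentation compared to placebo decreases the hazard of suicidal self-violence will be regarded as a positive result".

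The interim analysis follows the same pattern. SAP 10.1 and Protocol Section VII (Interim Analysis) give 0.34 as the hazard ratio under the interim alternative and set a 0.2% type I error. Both state that "the interim null hypothesis will be rejected if the hazard ratio exceeds $1/0.34 = 2.94$ or falls below 0.34".

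Elsewhere the same figures have a different role, and the decision rule is a p-value:

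- SAP Section 10 says "the test has 90% power to detect a hazard ratio of 1.64 or larger or 0.61 or less", and the sample size part of Protocol Section VII agrees.
- SAP Section 10 also says "the final primary hypothesis will be tested at $p=0.048$ level", with 0.002 for the interim test.
- Protocol Section VII (Primary Data Analysis Plan) says "the study of lithium will only be viewed as successful if patients augmented with lithium have a significantly lower hazard".
- SAP 10.2 (Futility Analysis) computes conditional power for a significant final result, using a normal critical value.

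**The concern.** A pair of lower and upper values attached to a statement of when the null is rejected reads as the rejection region. A hazard ratio that the test detects with 90% power cannot also be its critical value: if the truth sits at the cut-off, the estimate falls on either side of it about equally often, so power is about 50%. SAP 4.3 therefore holds two decision rules that disagree over a range of plausible results.

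At stake is how the primary result is read. An observed hazard ratio of 0.70 would be statistically significant and positive by the paragraph on interpretation, yet outside the written rejection region just above it. A pre-specified plan should not leave that open until after unblinding.

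**Working it through.** **Inputs.** One-year event rates 15% and 9.45% (SAP 4.3); 745 evaluable per arm and 182 events (SAP Table 2); test levels 0.048 and 0.002 (SAP Section 10); 373 per arm at the interim, 15% against 5.3% under the interim alternative, 112 events under the interim null (SAP 10.1).

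**Reproducing the plan's figures.**

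- Design hazard ratio: ln(1−0.0945)/ln(1−0.15) = 0.611.
- Events: 745 × (0.15 + 0.0945) = 182.
- Power at two-sided 0.048: 90.0% by the Freedman formula and 91.1% by Schoenfeld, against 90% stated.
- Table 2(a) by Freedman: 73.3%, 81.7% and 94.2% for reductions of 30%, 33% and 40%, against 73%, 81% and 94% stated.

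So the sample size and the power tables are built on the p-value rule.

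**Final boundary.** With 1:1 allocation the log hazard ratio has variance of about 4/D for D events, so the critical values are exp(∓2z/√D). With z = 1.977 and D = 182, 2 × 1.977/13.49 = 0.293, which gives 0.746 and 1.34. At 150 events the lower value is 0.724, and at 250 events 0.779.

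**What the written cut-off means at 182 events.** z = |ln HR| × √182/2.

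| Observed HR | z | Two-sided p |
|---|---|---|
| 0.61 | 3.33 | 0.0009 |
| 0.65 | 2.91 | 0.0037 |
| 0.70 | 2.41 | 0.016 |

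**Power under the two rules, normal approximation, true hazard ratio 0.611.**

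- p<0.048: Φ(0.493 × 6.745 − 1.977) = Φ(1.35) = 91%.
- HR<0.61: Φ((ln 0.61 − ln 0.611) × 6.745) = 50%.
- Difference: 41 percentage points.

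Simulating 20,000 trials (exponential times, one year, 745 per arm, log-rank) gave 90.9%, 49.8% and 41.1%.

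For a 33% reduction (hazard ratio 0.652, 187 events), the p-value rule gives 83% and the hazard-ratio rule 33%. The claim above Table 2, "This study will have greater than 80% statistical power at 5% overall error if the observed effect is as low as 33% reduction", therefore holds only under the p-value rule.

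**Interim boundary.** z = 3.090 for 0.002. The documents fix no interim event count, so three are shown.

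| Events | Basis | HR boundary for p<0.002 | p for an observed HR of 0.34 |
|---|---|---|---|
| 76 | interim alternative, 373 × (0.15 + 0.053) | 0.49 / 2.03 | 2.6 × 10⁻⁶ |
| 91 | design effect, 373 × (0.15 + 0.0945) | 0.52 / 1.91 | 2.7 × 10⁻⁷ |
| 112 | interim null, as stated | 0.56 / 1.79 | 1.1 × 10⁻⁸ |

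Power at level 0.002 for 15% against 5.3% is 89% (Freedman), 91% (two proportions) or 95% (Schoenfeld). So 0.34 is also a hazard ratio detectable with about 90% power. At the design effect with 91 events, p<0.002 is crossed about 23% of the time (simulation 21%) and HR<0.34 about 0.3% (simulation 0.5%).

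**The case against.** The best counter-argument is that the p-value rule plainly governs. The level is stated in the sentence before, the next paragraph defines positive and negative by significance, SAP Section 10 gives the test levels, and the SAS code in SAP 4.3 compares no hazard ratio with 0.61. SAP 4.3 also defines the alternative as a hazard ratio of 0.61 or lower, so the sentence may be loose shorthand for the design effect. On that reading the 50% and 41% figures describe an analyst who ignores everything else in the plan. Moreover, the written rule is the stricter one (two-sided type I error about 0.0009 at 182 events), so it cannot create a false positive.

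Most of this stands. The p-value rule is the intended one, and the 50% power applies only to a literal reading. The interim point is weaker still: both documents leave stopping guidelines to be agreed with the data monitoring committee, Protocol XVII (Premature Termination of the Study) describes the boundary by significance level, and the reading of 0.34 as a detectable effect is inferred from the calculation because no interim power is stated.

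What does not stand is that evident intent makes the wording harmless. This sentence is the one in the primary-efficacy section that says when the null is rejected, and its threshold is wrong.

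**Conclusion.** The concern holds, as an error in three sentences rather than in the design. The values 0.61/1.64 and 0.34/2.94 are detectable effects presented as critical values. The planned tests, their levels, the sample size and the 90% power are unaffected.

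The practical exposure is a final hazard ratio between 0.61 and about 0.75, where the plan gives two answers; that is where about 41% of trials would fall if the design effect were true. The error runs towards missing or disputing a real effect, not towards a false claim. At the interim the harm is limited, though a committee handed 0.34 as the boundary would be misled.

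These figures assume the large-sample variance 4/D, 1:1 allocation, proportional hazards and the planned 182 events at the final analysis. The hazard-ratio equivalents move with the observed event count.

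**What to change.** Reword the rejection sentence in SAP 4.3, the one in SAP 10.1, and its twin in Protocol Section VII (Interim Analysis):

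- Rejection rests only on the two-sided log-rank p-value: below 0.048 at the final analysis, below 0.002 at the interim.
- Describe 0.61/1.64 and 0.34/2.94 as the effects the tests are powered to detect, as SAP Section 10 and the Protocol's sample size section already do for 0.61.
- If hazard-ratio equivalents are kept for orientation, mark them as approximate and dependent on the event count: about 0.75/1.34 at 182 final events, and about 0.52/1.91 at 91 interim events (0.49/2.03 at 76, 0.56/1.79 at 112).

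The cost is the wording of two SAP sentences and one Protocol sentence. No test, level, sample size or data collection changes.

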There have been two recent randomized clinical trials of lithium for preventing suicide attempts in patients who survived an initial attempt. Both were unable to enroll their target number of participants. As a result, both were inadequately powered and neither was definitive. One study evaluated adjunctive treatment for preventing repeated suicide attempts in depression, but it was terminated prematurely after only 167 of the planned 468 subjects were enrolled. In this study, Lauterbach and colleagues (2008) reported a hazard ratio for lithium of 0.517 that, as expected given the reduced sample size, was not significant (95% CI 0.18-1.43). In the second study, Oquendo and co-investigators (2011) evaluated lithium versus valproate for treatment of bipolar disorder in patients with previous suicide attempts. It reported negative results for the prevention of repeated attempts after 2.5 years for 98 of a planned 232 randomized subjects. Post-hoc sample size calculations showed the study had 80% power for detecting an 85% reduction for lithium relative to valproate. Additional post-hoc calculations by CSP-590 investigators demonstrate that the study would have had only 14.4% power for detecting a 50% effect, and only 9.3% power for a 40% effect. The negative results provide evidence against only a very large effect. The raw data indicate that 16% of the valproate group reattempted over 2.5 years; reattempts for those on lithium were 33% lower at 1 year and 25% lower at the conclusion of the study.

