If a medical center is placed on probation, the Study Chair will confer with the site personnel and may visit the site, if necessary, to help improve the rate of recruitment. Once a site is placed on probation, failure to meet the requirements specified by the end of the probation period will result in a recommendation for termination. Additionally, sites that fail to meet two or more of

the above performance measures, and sites that habitually under-perform by any of these measures, will be at risk of termination.

To plan for the possible termination of a site(s) and the addition of a new site(s), back-up sites with IRB approval will be identified prior to study initiation to minimize the delay in adding a new site. The Executive Committee will take actions leading to discontinuation of a site only with the concurrence of the CSPCC Director. If a site is terminated from the trial, resources will be reallocated to other medical centers or used to start up a back-up site.

III. Premature Termination of the Study

The Director, CSP, can terminate a cooperative study before completion. The DMC makes recommendations as to whether the study should continue or be terminated. The decision to terminate a study prematurely is a complex one involving many factors. The DMC may consider the following circumstances as grounds for early termination:

1. If patient accrual falls far below that which is predicted (e.g., 75% of expected accrual), it will be necessary to reassess the study design and the potential value of its continuation.
2. If patient accrual far exceeds the predicted, this study could be completed at an earlier date.
3. If serious adverse events or mortality are noted to be excessive in either treatment group.
4. If interim analyses indicate a trend in the data which is unlikely to change prior to study completion.
5. If, during interim analyses on the primary end point, the significance level crosses the efficacy boundary established by the DMC.

Termination by recommendation of the DMC will be carried out as outlined in CSP guidelines.

XVIII. GOOD CLINICAL PRACTICES AND SITE REVIEW PROGRAM

Role of GCP

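### SAP 4.3 pre-assigns one label, negative, to both a non-significant result and significant harm, and does not use the planned confidence interval to separate a result that excludes the design effect from one that does not (minor)

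*SAP*

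**What the plan says.** SAP 4.3 specifies a "two sided log rank test at 90% power and 4.8% Type I error", and SAP section 10 repeats that "the final primary hypothesis will be tested at $p=0.048$ level". The design alternative is a "hazard ratio for lithium therapy compared to control therapy lower than or equal to 0.61".

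SAP 4.3 then names the possible outcomes. Only a significant reduction in hazard is positive. A result in which lithium "does not significantly differ from placebo or significantly increases the hazard rate relative to placebo will be regarded as a negative result". There is no third category.

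The next sentence of SAP 4.3 plans a Cox model giving the hazard ratio and its 95% confidence interval. Neither document compares that interval with 0.61 or any other value. SAP 10.2 covers conditional power at the interim and does not classify the final result. Protocol VII (Primary Data Analysis Plan) defines only success, as a significantly lower hazard on lithium. The negative label for non-significance is therefore the SAP's own.

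Just before the outcome labels, SAP 4.3 also says the null will be rejected if the hazard ratio is above 1.64 or below 0.61.

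**The concern.** In a superiority trial, a non-significant test means that benefit was not shown. Whether the effect the trial was built to find has been ruled out is a separate question, and the confidence interval answers it. The SAP's rule gives the same name to an interval that excludes 0.61 and to one that contains both 0.61 and 1. It also gives that name to significant harm, a direction the two-sided test was chosen to allow for.

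Protocol I (Clinical Pharmacology of Lithium for Suicide Prevention) makes the distinction when it reads an earlier under-recruited lithium trial: "The negative results provide evidence against only a very large effect". The SAP's rule for this trial's own result does not make it.

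At stake is the wording of the trial's conclusion. It matters most if events fall short. Protocol XVII (Premature Termination of the Study) foresees a shortfall: "If patient accrual falls far below that which is predicted (e.g., 75% of expected accrual" is the example given for reassessing the design and the value of continuing.

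**Working it through.** **Inputs.** Event rates: "15% re-attempt rate in the placebo group and 9.45% re-attempt rate in the lithium group" (SAP 10). Sample: attrition "resulting in an analytic sample of 1490 evaluable subjects", 745 per arm (SAP 10). Final two-sided level 0.048 (SAP 4.3 and 10), so z = 1.977. Design hazard ratio 0.61 (SAP 4.3). Events: 182 as planned, and 121 in the row of SAP Table 2(c) with a 10% placebo rate.

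**1. Reproduce the plan's figure.**
- HR = ln(1 − 0.0945) / ln(1 − 0.15) = 0.611.
- Expected events = 745 × (0.15 + 0.0945) = 182.2.
- Freedman's formula: [(1.977 + 1.282) × (1 + 0.611)/(1 − 0.611)]² ≈ 182 events for 90% power.
- 182 / 0.12225 ≈ 1,489 evaluable, and 1490 / 0.8 = 1862.5.

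The design figures hold.

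**2. Find the zone that is non-significant but does not exclude 0.61.** Use SE(ln HR) = 2/√events.
- Significance is reached at an observed HR of C = exp(−1.977 × SE) or lower.
- The lower 95% limit passes 0.61 only when the observed HR is above U = 0.61 × exp(1.96 × SE).
- Observed values between C and U are non-significant and still compatible with 0.61.

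At 182 events, SE = 0.148, C = 0.746 and U = 0.816. For example, an observed HR of 0.78 has a 95% interval of 0.58 to 1.04.

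**3. Chance of landing in the zone.** For true hazard ratio θ it is Φ[(ln U − ln θ)/SE] − Φ[(ln C − ln θ)/SE]. At 182 events with θ = 0.61 this is Φ(1.96) − Φ(1.357) = 0.975 − 0.913 = 0.062. With θ = 0.70 it is Φ(1.032) − Φ(0.428) = 0.849 − 0.666 = 0.183.

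| Events | Zone of observed HR | True HR 0.61 | True HR 0.70 |
|---|---|---|---|
| 182 (plan) | 0.746–0.816 | 6% | 18% |
| 121 (SAP Table 2(c)) | 0.698–0.871 | 20% | 39% |
| 91 (assumption: half the planned events) | 0.661–0.920 | 33% | 51% |

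The documents give no event count for an early stop, so the last row only illustrates the trend.

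**4. Effect of the confidence level.** A 95.2% interval, which matches the 0.048 test, moves U at 182 events from 0.816 to 0.818. The two chances change from 6.2% to 6.3% and from 18.3% to 18.7%.

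**5. The adjoining rejection bound.** At 182 events the 0.048 log-rank test is significant at an observed HR of about 0.746, not 0.61. As a literal cut-off, 0.61 corresponds to z = ln(0.61)/0.148 = −3.33. That is a two-sided level of about 0.0009, with about a 50% chance of rejection when the true HR is 0.611. Observed ratios between 0.61 and 0.746 would be significant by the test but not rejected by the bound.

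**6. A caution on mixing figures.** The normal approximation in step 2 gives 8.7% and 22.9% non-significant results at 182 and 121 events when the true HR is 0.61. SAP Table 2 implies 10% and 27%. The approximations differ, and the 121-event row (10% against 6.3%) corresponds to an HR of 0.618 rather than 0.61. The zone percentages should be read as approximate.

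**The case against.** The best defence is that *negative* here may mean only *not positive*. SAP 4.3 does not say that lithium lacks the target effect, and its label is the complement of the protocol's success criterion. Protocol I itself calls results of underpowered studies negative while noting their limited power. A reader might infer that the SAP commits the investigators to concluding that lithium does not work; the documents do not support that.

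Three other strong readings also fail.
- Harm would not be hidden. The hazard ratio and interval show direction, SAP 7.4 reports suicide reattempt and mortality rates by arm, and Protocol XVII makes excess serious adverse events or mortality a ground for stopping.
- The trial is not planned with fewer events. SAP Table 2 (Protocol Table 3) is a power sensitivity table, and the plan is 182.
- Low accrual does not trigger an automatic stop. It is a circumstance that the Data Monitoring Committee may consider.

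It is also fair to say that 0.61 is not a smallest worthwhile effect; the documents define none. At 182 events an observed HR of 0.83 has a 95% interval of about 0.62 to 1.11, which excludes 0.61 but not a 35% reduction in hazard. The dividing line therefore speaks only to the design alternative.

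What remains is narrower. The SAP states a rule, that rule puts two different findings under one name, and it does not use an interval that is already planned.

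**Conclusion.** The point holds, as a minor one. It concerns a pre-specified conclusion, not missing information: the test, its error rate, the estimate and the success criterion are untouched. At 182 events the affected results are observed hazard ratios of about 0.75 to 0.82, which occur in roughly 6% of trials if the true ratio is 0.61 and 18% if it is 0.70. The zone grows to about 0.70 to 0.87 (20% and 39%) at 121 events.

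These figures assume 1:1 allocation, proportional hazards, a normal approximation for ln HR with SE = 2/√events, and significance decided by the log-rank p-value. They do not apply if the 0.61 bound is read literally as the rejection rule, which is one more reason to remove it.

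**What to change.** In SAP 4.3, replace the outcome sentence with four categories, significance being judged by the log-rank test at 0.048:

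- **Positive:** significant, HR below 1. This remains the only success.
- **Harm:** significant, HR above 1.
- **Negative for the design effect:** not significant, and the lower confidence limit is above 0.61.
- **Inconclusive for the design effect:** not significant, and the lower limit is 0.61 or less.

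State that 0.61 is the design alternative and not a smallest worthwhile effect. It corresponds to a 37% relative reduction at a 15% placebo rate; at a 10% rate the matching hazard ratio is ln(0.937)/ln(0.90) = 0.618. Use a 95.2% interval for this classification so that it agrees with the 0.048 test.

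In the same section, replace rejection at a hazard ratio above 1.64 or below 0.61 with rejection at log-rank p < 0.048, and keep 0.61 as the effect the trial is powered to detect.

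The cost is a few sentences and a changed confidence level in the Cox output, with no new data or model and no change to type I error or power. The downside is that some non-significant results will have to be reported as inconclusive rather than negative. The wording should be settled before unblinding.
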